## 5 Treatment

### 5.1 Study treatment

#### 5.1.1 Investigational and control drugs

The sponsor will provide single-blind study medication for Epoch 2:

- LIK066-matching placebo tablets

- Empagliflozin-matching placebo capsules (tablets over-encapsulated)

The sponsor will provide double-blind study medication for Epoch 3 and Epoch 4:

- LIK066 2.5mg film-coated tablets
- LIK066 10mg film-coated tablets
- LIK066 50mg film-coated tablets
- LIK066-matching placebo tablets
- Empagliflozin 10mg film-coated tablets (over-encapsulated)
- Empagliflozin 25mg film-coated tablets (over-encapsulated)
- Empagliflozin-matching placebo capsules (tablets over-encapsulated)

For each treatment arm (see [Section 5.2](#)), patients will receive a combination of one tablet and one capsule as described above. All patients will take the study medication as explained in [Section 5.5.4](#), and the dose regimens will be prepared for each treatment arm in medication wallets.

No other drugs will be supplied. Sufficient medication will be supplied for treatment according to the study protocol.

### **5.1.2 Additional treatment**

No additional treatment beyond investigational drug and control drug are included in this study.

## **5.2 Treatment arms**

All patients entering Epoch 2 (run-in) will receive single-blind placebo (see [Section 3.1.2](#)& [Section 5.5.4](#)).

At visit 201 (randomization), patients eligible for randomization will be assigned to one of the following 5 treatment arms in Epoch 3 (see [3.1.3 Epoch 3 \(treatment\)](#)) in a ratio of 1:1:2:2:2:

- 2.5mg qd LIK066
- 10mg qd LIK066
- 50mg qd LIK066
- 10mg qd empagliflozin up-titrated to 25mg qd after 2 weeks
- Placebo qd

In Epoch 4 (see [3.1.4 Epoch 4 \(treatment\)](#)), patients will continue to receive the treatment they were assigned to in Epoch 3.

## **5.3 Treatment assignment and randomization**

At Visit 201 (randomization) all eligible patients will be randomized via Interactive Response Technology (IRT) to one of the treatment arms. The investigator or his/her delegate will contact the IRT after confirming that the patient fulfills all the inclusion/exclusion criteria. The IRT

will assign a randomization number to the patient, which will be used to link the patient to a treatment arm and will specify a unique medication number for the first package of study drug to be dispensed to the patient. The randomization number will not be communicated to the user of the IRT system.

The randomization numbers will be generated using the following procedure to ensure that treatment assignment is unbiased and concealed from patients and investigator staff. A patient randomization list will be produced by the IRT provider using a validated system that automates the random assignment of patient numbers to randomization numbers. These randomization numbers are linked to the different treatment arms, which in turn are linked to medication numbers. A separate medication list will be produced by or under the responsibility of Novartis drug supply management using a validated system that automates the random assignment of medication numbers to packs containing the investigational drug(s).

The randomization scheme for patients will be reviewed and approved by a member of the Novartis randomization group.

Randomization will be stratified according to geographical region and LVEF (< 45% versus  $\geq$  45%), see [Section 3.1.3](#).

## 5.4 Treatment blinding

Patients, investigator staff, Novartis study team, persons performing the assessments, and data analysts will remain blind to the identity of the treatment from the time of randomization until database lock, using the following methods:

1. Randomization data are kept strictly confidential until the time of unblinding, and will not be accessible by anyone else involved in the study with the following exceptions: the randomization codes associated with patients from whom PK samples are taken will be disclosed to PK analysts who will keep the PK results confidential until database lock.
2. The identity of the treatments will be concealed by the use of study drug that are all identical in packaging, labeling, schedule of administration, appearance, taste and odor. A double dummy design will be used as the identity of the study drugs cannot be disguised due to their different forms.

Unmasking will only occur in the case of patient emergencies (see [Section 5.5.9](#)), at the time of the Week 12 analysis and at the conclusion of the study.

The analysis group (statisticians/programmers), who will be unmasked to perform the Week 12 analysis, will not be involved in any study conduct activities related to the study Week 12 to Week 36 period (Epoch 4) after the unmasking. A separate analysis group, who does not have access to the analysis results and the identity of treatments at Week 12 analysis, will perform the pre-planned final analysis at the end of the study.

The core study team (including the study leader(s), study physician and data manager), who are directly involved in study conduct activities during the study Week 12 to Week 36 period (Epoch 4), will not have access to the patient level data with identity of treatments such as patient listings at Week 12 analysis.

The Week 12 analysis results and the identity of treatments will not be shared with the study site personnel until after the final database lock at the end of study.

## **5.5 Treating the patient**

Sponsor qualified medical personnel will be readily available to advise on trial related medical questions or problems.

### **5.5.1 Patient numbering**

Each patient is uniquely identified in the study by a combination of his/her center number and patient number. The center number is assigned by Novartis to the investigative site. Upon signing the pre-screening or study informed consent form, the patient is assigned a patient number by the investigator. At each site, the first patient is assigned patient number 1, and subsequent patients/subjects are assigned consecutive numbers (e.g. the second patient is assigned patient number 2, the third patient is assigned patient number 3). At screening (Visit 1) the investigator or his/her staff will contact the IRT and provide the requested identifying information for the patient to register them into the IRT. For studies using eCRFs, only the assigned patient number must be entered in the field labeled "Patient ID" on the EDC data entry screen (e.g. enter '1', '2', etc.). Once assigned to a patient, the patient number will not be reused. If the patient fails to be randomized for any reason, the IRT must be notified within 2 days that the patient was not randomized. The reason for not being randomized will be entered on the Screening Log, and the Demography eCRF should also be completed.

### **5.5.2 Dispensing the study drug**

Each study site will be supplied with study drug in packaging of identical appearance.

The study drug packaging has a 2-part label. A unique medication number is printed on each part of this label which corresponds to one of the treatment arms. Investigator staff will identify the study drug package(s) to dispense to the patient by contacting the IRT and obtaining the medication number(s). Immediately before dispensing the package to the patient, investigator staff will detach the outer part of the label from the packaging and affix it to the source document (Drug Label Form) for that patient's unique patient number.

### **5.5.3 Handling of study and additional treatment**

#### **5.5.3.1 Handling of study treatment**

Study treatment must be received by a designated person at the study site, handled and stored safely and properly, and kept in a secured location to which only the investigator and designees have access. Upon receipt, all study treatment must be stored according to the instructions specified on the labels. Clinical supplies are to be dispensed only in accordance with the protocol. Technical complaints are to be reported to the respective Novartis CPO Quality Assurance.

Medication labels will be in the local language and comply with the legal requirements of each country. They will include storage conditions for the study treatment but no information about the patient except for the medication number.

The investigator must maintain an accurate record of the shipment and dispensing of study treatment in a drug accountability log. Monitoring of drug accountability will be performed by monitors during site visits or remotely and at the completion of the trial. Patients will be asked

to return all unused study treatment and packaging at each study visit and where applicable, at the time of discontinuation of study treatment.

At the conclusion of the study, and as appropriate during the course of the study, the investigator will return all unused study treatment, packaging, drug labels, and a copy of the completed drug accountability log to the Novartis monitor or to the Novartis address provided in the investigator folder at each site.

#### **5.5.3.2 Handling of additional treatment**

Not applicable.

#### **5.5.4 Instructions for prescribing and taking study treatment**

The patients have to take study medication, 1 capsule in the morning, with or without food, and 1 tablet at bedtime.

All prescribed dosages and all dose changes during the study must be recorded on the appropriate study drug Dosage Administration Record eCRF. All kits of study treatment assigned by the IRT will be recorded/databased in the IRT.

During each study visit, the investigator should encourage compliance with study medication by instructing the patient to take the study drug exactly as prescribed to maintain the validity of the study and to optimize any potential effect of the study drug regimen. The patient should be instructed to contact the investigator if he/she is unable for any reason to take the study drug regimen as prescribed.

On study visit days, the patients must take their study medication or their anti-diabetic treatment only after blood draws have been done.

#### **5.5.5 Permitted dose adjustments and interruptions of study treatment**

Study drug dose adjustments and/or interruptions are not permitted, unless done for safety reasons (see [Section 7.1](#)).

#### **5.5.6 Rescue medication**

During Epoch 3 and Epoch 4, rescue medication may be used in addition to ongoing study medication for those patients whose glycemic control is deteriorating. The patient must come in for an unscheduled visit to have a sample drawn for FPG and HbA1c measurement performed by the central laboratory if:

- Self-measured FPG on three consecutive occasions exceeds the limits in [Table 5-1](#).
- The FPG result from a blood sample analyzed at the central laboratory exceeds the limits described in [Table 5-1](#).

**Table 5-1      Rescue criteria for FPG or HbA1c**

Timeframe	Parameter	Value	Action
Between V201 (Randomization) and V204 (Week 8)	FPG	>240mg/dL (13.3mM)	Unscheduled visit for central lab parameter measurement.
Between V204 (Week 8) and V301 (Week 12)	FPG	>220mg/dL (12.2mM)	If elevation confirmed by central lab: background OAD to escalate to the maximum approved dose, followed by addition of insulin as per the investigator's discretion.
Between V301 (Week 12) and V399 (Week 36)	FPG	>200mg/dL (11.1mM)	
Between V301 (Week 12) and V399 (Week 36)	HbA1c	>8%	

If the results confirm the exceeded limits, the background OAD should be initially escalated to the maximal approved dose, followed by addition of rescue medication.

Rescue medication, preferably insulin, should be used according to the local label and must be provided locally.

Rescued patients will continue to participate in the study to allow for assessment of exposure and safety of LIK066.

Use of rescue medication must be recorded on the Rescue Medication eCRF.

### **5.5.7      Concomitant medication**

The investigator must instruct the patient to notify the study site about any new medications he/she takes after the patient was enrolled into the study. All medications, procedures and significant non-drug therapies (including physical therapy and blood transfusions) administered after the patient was enrolled into the study must be recorded in the Concomitant Medications / Surgical and Medical Procedures eCRF.

Every effort should be made by the Investigator to keep the dose level of each patient's allowed background heart failure medications stable throughout the entire study duration. However; if the clinical condition of the patient warrants a change in any of these medications, it is allowed at the discretion of the study Investigator.

Each concomitant drug must be individually assessed against all exclusion criteria/prohibited medication. If in doubt the investigator should contact the Novartis medical monitor before randomizing a patient or allowing a new medication to be started.

### **5.5.8      Prohibited medication**

Use of the treatments displayed in [Table 5-2](#) is not allowed after patients have become eligible for participation into the study. At the latest, patients should stop using the medications listed in [Table 5-2](#) at the start of Epoch 2.

**Table 5-2 Prohibited medication**

Medication/product	Prohibition period	Action taken
St. John's wort (strong CYP3A inducer)	Entire study (from V1 until end-of-study)	Discontinue treatment during the screening period once patient is eligible for participation in the study.
SGLT inhibitors other than study medication	Entire study (and up to 2 months before Visit 1)	SGLTi has to be stopped immediately, otherwise the patients has to be discontinued from study medication

Some medications or products must be used with caution:

- Use of grapefruit juice (strong inhibitor of CYP3A4) should be discouraged and its consumption must not happen within 2h of study medication intake.
- Use of antibiotic or antifungal medications that are strong inhibitors of CYP3A4 should be limited to 10 days during the study and must not be used at the time of randomization. Examples of such medications are clarithromycin, telithromycin, itraconazole, ketoconazole, voriconazole or posaconazole.
- Use of UGT inhibitors such as probenecid, valproic acid or mefenamic acid should be limited to 10 days during the study and must not be used at the time of randomization.

### **5.5.9 Emergency breaking of assigned treatment code**

Emergency code breaks must only be undertaken when it is required to in order to treat the patient safely. Most often, study treatment discontinuation and knowledge of the possible treatment assignments are sufficient to treat a study patient who presents with an emergency condition. Emergency treatment code breaks are performed using the IRT. When the investigator contacts the system to break a treatment code for a patient, he/she must provide the requested patient identifying information and confirm the necessity to break the treatment code for the patient. The investigator will then receive details of the investigational drug treatment for the specified patient and communication confirming this information. The system will automatically inform the Novartis monitor for the site and the Study Team that the code has been broken.

It is the investigator's responsibility to ensure that there is a dependable procedure in place to allow access to the IRT system at any time in case of emergency. The investigator will provide the protocol number, the study drug name (if available) and the patient number.

In addition, oral and written information to the patient must be provided on how to contact the investigator's backup in cases of emergency, or when the investigator is unavailable, to ensure that un-blinding can be performed at any time.

Patients whose treatment has been unmasked must be discontinued from study treatment (see [Section 5.6.2](#)).

## **5.6 Study completion and discontinuation**

### **5.6.1 Study completion and post-study treatment**

A patient will be considered to have completed the study when the patient has completed the last planned visit (see [Table 6-1](#)). The study as a whole will be considered completed when all randomized subjects have completed the last visit planned in the protocol or have discontinued the study prematurely.

For subjects who are lost to follow-up, see [Section 5.6.4](#).

The investigator must provide follow-up medical care for all subjects who are prematurely withdrawn from the study, or must refer them for appropriate ongoing care.

### **5.6.2 Discontinuation of study treatment**

Discontinuation of study treatment for a patient occurs when study drug is stopped earlier than the protocol planned duration, and can be initiated by either the patient or the investigator.

The investigator must discontinue study treatment for a given patient if, on balance, he/she believes that continuation would negatively impact the risk/benefit of trial participation.

Study treatment must be discontinued under the following circumstances:

- Patient wish
- Pregnancy (see [Section 6.5.6](#) and [Section 7.6](#))
- Use of prohibited treatment see [Table 5-2](#)
- Any situation in which study participation might result in a safety risk to the patient
- Emergence of the following adverse event: Ketoacidosis, diabetic foot ulcer or lower limb amputation (including toe amputation)
- Any laboratory abnormalities that in the judgment of the investigator, taking into consideration the patient's overall status, prevents the patient from continuing participation in the study
- Patients whose study treatment has been unmasked (see [Section 5.5.9](#))
- Withdrawal of consent (see [Section 5.6.3](#))

If discontinuation of study treatment occurs, the patient should NOT be considered withdrawn from the study. The patient should return to the clinic as soon as possible, after discontinuation of study drug, for a study treatment discontinuation visit (see [Table 6-1](#)). Treatment discontinuation visit assessments detailed in [Table 6-1](#) should be completed and recorded in the eCRF. The investigator must determine the primary reason for the patient's premature discontinuation of study treatment and record this information on the appropriate eCRF.

After study treatment discontinuation, at a minimum, in abbreviated visits, the following data should to be collected at clinic visits or via telephone visits:

- new / concomitant treatments
- adverse events/Serious Adverse Events

If the patient cannot or is unwilling to attend any visit(s), the site staff should maintain regular telephone contact with the patient, or with a person pre-designated by the patient. This telephone contact should preferably be done according to the study visit schedule.

Patients who discontinue study medication during Epoch 3 should be followed-up until they discontinue the study at the end of Epoch 3 (V299).

The investigator must also contact the IRT to register the patient's discontinuation from study treatment.

If study drug discontinuation occurs because treatment code has been broken, please refer to [Section 5.5.9](#)

### **5.6.3 Withdrawal of informed consent**

Patients may voluntarily withdraw consent to participate in the study for any reason at any time. Withdrawal of consent from the study is defined as when all of the following applies:

- A patient does not want to participate in the study anymore  
and
- does not want any further visits or assessments  
and
- does not want any further study related contacts  
and
- does not allow analysis of already obtained biologic material

In this situation, the investigator must make every effort (e.g. telephone, e-mail, letter) to determine the primary reason for the patient's decision to withdraw his/her consent and record this information.

Study treatment must be discontinued and no further assessments conducted, and the data that would have been collected at subsequent visits will be considered missing.

Further attempts to contact the patient are not allowed unless safety findings require communicating or follow-up.

All efforts should be made to complete the assessments prior to study withdrawal.

A final evaluation at the time of the patient's study withdrawal should be made as detailed in [Table 6-1](#).

### **5.6.4 Lost to follow-up**

For patients whose status is unclear because they fail to appear for study visits without stating an intention to discontinue or withdraw, the investigator should show "due diligence" by documenting in the source documents steps taken to contact the patient, e.g. dates of telephone calls, registered letters, etc. A patient cannot be considered as lost to follow-up until the time point of his/her scheduled end of study visit has passed.

### **5.6.5 Early study termination by the sponsor**

The study can be terminated by Novartis at any time for any reason. This may include reasons related to the benefit risk assessment of participating in the study, practical reasons, or for regulatory or medical reasons (including slow enrolment). Should this be necessary, the patient must be seen as soon as possible and treated as a prematurely withdrawn patient. The investigator may be informed of additional procedures to be followed in order to ensure that adequate consideration is given to the protection of the patient's interests. The investigator will be responsible for informing the Institutional Review Board/Independent Ethics Committee (IRBs/IECs) of the early termination of the trial.

## **6 Visit schedule and assessments**

[Table 6-1](#) lists all of the study visits and assessments and indicates with an “X” when the assessments are performed.

Patients must be seen for all visits on the designated day, or as close to it as possible. Missed or rescheduled visits should not lead to automatic discontinuation. Patients who prematurely discontinue the study for any reason should be scheduled for a visit as soon as possible, at which time all of the assessments listed for the final visit will be performed. At this final visit, all dispensed investigational product should be reconciled and the adverse event and concomitant medications reconciled on the eCRF.

Patients will be contacted for safety evaluations during the 30 days following the last administration of study treatment.

**Table 6-1 Assessment schedule**

Epoch		1	2		3					4		
Visit	Pre-screen	1 Screen	101 Run-in	199 TD/ PPD	201 RND/ BL	202	203	204	299 TD A / PPD	301	302	399 TD A / PPD/ EOS
Week		-4	-2	0	2	4	8	12	24	36		
Screening assessments												
Pre-screening informed consent	S P											
Study informed consent		X										
Inclusion/exclusion (Section 4)		X		X*	X*							
Patient demographics (Section 6.2)		X										
Medical history		X										
Medical history: protocol solicited & Heart Failure/Diabetes		X										
Smoking & alcohol history (Section 6.2)		X										
Efficacy												
Height (Section 6.4.1)		X										
Weight / BMI (Section 6.4.1)		X C	X		X	X	X	X	X	X	X	X
Blood pressure (Section 6.4.8)		X	X		X	X	X	X	X	X	X	X
NYHA classification (see Section 6.4.4)		X	X		X	X	X	X	X	X	X	X
Body composition: bio-impedance (see Section 6.4.3)					X				X	X		X
Echocardiography (see Section 6.4.5)			X							X D		X D
NT-ProBNP (Section 6.4.2)	S P	X			X		X B		X B	X B		X B

Epoch		1	2	3					4			
Visit	Pre-screen	1 Screen	101 Run-in	199 TD/ PPD	201 RND/ BL	202	203	204	299 TD A / PPD	301	302	399 TD A / PPD/ EOS
Week		-4	-2	0	2	4	8	12	24	36		
Epoch 3 phase disposition								X				
Study completion												X
Sub-studies (subset of patients)												
Sub-study 1: DXA ( Section 6.4.3 & Section 6.5.5 ): Body composition/BMD					X					X D		X D
Sub-study 2: 24h urine collection ( Section 6.4.10 ) Bone biomarkers ( Section 6.5.3.4 ) Renal biomarkers ( Section 6.5.3.4 )					X				X G	X G		X G

RND = Randomization visit;

EOS = End of Study;

TD = study treatment discontinuation;

PPD = premature patient discontinuation;

X = assessment to be recorded on clinical data base;

S = assessment to be recorded on source documentation only;

\* = reassessed prior to randomization;

A = patients only discontinuing study medication need to have such assessments done per unplanned assessment eCRF;

B = laboratory values will be blinded;

C = BMI will be calculated at Visit 1;

D = no echocardiography/DXA assessment for patients <12 weeks after Visit 201 with PPD/TD. If week 12 echocardiography/DXA done before PPD/TD, no repeat echocardiography/DXA needed for patients < 24 weeks after Visit 201;

G = urinary glucose values will be blinded;

T = only triglycerides

P = pre-screening for NT-proBNP, HbA1c, eGFR and serum potassium is optional (the pre-screening data will be handled as source documentation only). These laboratory parameters will be assessed from all patients by the central laboratory at Visit 1, independently whether or not pre-screening was done. At Visit 1, SAEs are to be collected from pre-screened patients only if the SAE is reported to be causally related with study procedures (i.e. blood sampling).

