2.6.2.3 Laboratory data

2.6.2.3.1 Hematology, Biochemistry and Urinalysis

Each laboratory parameter in [Table 2-3](#) will be summarized descriptively by visit and treatment group for actual and change from baseline values. The summary will be provided separately for biochemistry, hematology and urinalysis laboratory parameters.

Shift tables based on the standard ranges for each laboratory parameters will be provided by treatment group at each visit to present incidence of transitions from a baseline high, normal or low laboratory value to a post-baseline high, normal or low value.

The number and percentage of patients with clinically notable laboratory results post baseline will be presented in accordance with [Table 2-4](#).

Table 2-3 Laboratory parameters

Category	Parameter(s)
Hematology	RBC (total), WBC (total), platelet count (direct), hemoglobin, hematocrit, basophils (absolute, %), eosinophils (absolute, %), lymphocytes (absolute, %), monocytes (absolute, %), neutrophils (absolute, %)
Biochemistry	ALT, albumin, alkaline phosphatase (ALP), AST, bicarbonates, bilirubin (direct, total), blood urea nitrogen (BUN), calcium (total), chloride (Cl ⁻), creatinine, cystatin C, eGFR (MDRD), magnesium (Mg ²⁺), phosphates, potassium (K ⁺), protein (total), sodium (Na ⁺), uric acid, γ-GT, amylase, lipase, serum ketones and beta hydroxybutyrate
Urinalysis	pH, specific gravity, protein, glucose, ketones, nitrites, blood, leucocytes
Urinalysis	UACR Urine albumin to creatinine ratio (spot urine), cystatin C/creatinine ratio (spot urine)

Table 2-4 Clinically notable laboratory values

Parameter	Criteria (based on a percent change from baseline)
Hematology	
RBC (total)	>50% increase, >20% decrease
WBC (total)	>50% increase, >50% decrease
Platelet count	>75% increase, >50% decrease
Hemoglobin	>50% increase, >20% decrease
Hematocrit	>50% increase, >20% decrease
Clinical chemistry	
ALT	>150% increase
AST	>150% increase
BUN	≥50% increase
Creatinine	>50% increase
Total bilirubin	>100% increase
ALP	>100% increase
Sodium	>5% increase or >150, or decrease <130 mmol/L

Potassium	absolute values < 3.0 mmol/L, > 5.9 mmol/L
Chloride	>10% increase, >10% decrease
Calcium	>10% increase, >10% decrease and hyper - > 2.6,
Uric acid	>50% increase
Plasma glucose	>50% increase
Plasma glucose	< 3.0 mmol/L (54 mg/dL)

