2.6.2.4 Vital signs

Sitting systolic blood pressure (SBP), sitting diastolic blood pressure (DBP) and sitting pulse will be descriptively summarized (by n, mean, standard deviation, median, Q1, Q3, minimum and maximum) for actual value and change from baseline values for each scheduled assessment visit and treatment group. A listing of all patients with notable vital sign values and changes (as defined in [Table 2-6](#)) will be provided.

Table 2-6 Vital signs notable range deviations

Vital sign	Notable abnormalities	
Pulse (beats/min)		either ≥ 120 + increase $\geq 25^*$ or > 130 either ≤ 50 + decrease $\geq 30^*$ or < 40
BP (mmHg)	systolic	either ≥ 180 + increase $\geq 30^*$ or > 200 either ≤ 90 + decrease $\geq 30^*$ or < 75
	diastolic	either ≥ 105 + increase $\geq 20^*$ or > 115 either ≤ 50 + decrease $\geq 20^*$ or < 40

* Refers to post-BL value as compared to BL value.

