2.6.2.5 ECG

The following variables will be descriptively summarized by visit and treatment: QTcF duration (msec), heart rate (beats/min), PR duration (msec), RR duration (msec), and QRS duration (msec).

The number and percentage of patients meeting the following criteria will be summarized by visit and treatment group for the double-blind period:

- QTcF > 500 msec
- QTcF > 480 msec
- QTcF > 450 msec
- QTcF increases from baseline \geq 30 msec
- QTcF increases from baseline \geq 60 msec
- PR > 200 and \leq 220 msec
- PR > 220 msec
- PR increases from baseline > 25% (PR > 200 msec)
- QRS > 110 and \leq 120 msec
- QRS > 120 msec
- QRS changes from baseline > 25 % (QRS > 110 msec)
- Heart rate > 100 beats/min
- Heart rate < 50 beats/min

In addition, a visit-based shift table will be provided to summarize the shifting from BL for each ECG parameter.

Cutoff points below are used to define normal or abnormal criteria in the above ECG shift table:

- QTcF: >450 or $=<$ 450 msec for male, or, >460 or $=<$ 460 msec for female
- QRS: >120 or $=<$ 120 msec
- PR: >200 or $=<$ 200 msec
- HR: >100 or $=<$ 100 beats/min

A listing of ECG parameters together with newly occurring or worsening abnormalities will be provided.

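### ECG outliers and laboratory shifts are tabulated only by visit, with no any-time count per arm and no rule for unplanned assessments made when a patient stops drug but stays in the study

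*Protocol*

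**What the plan says.** **Stopping drug.** Protocol 5.6.2 separates stopping drug from leaving the study: "If discontinuation of study treatment occurs, the patient should NOT be considered withdrawn from the study". The patient returns for a treatment discontinuation (TD) visit as soon as possible. Table 6-1 attaches footnote A to TD at Visits 299 and 399: "patients only discontinuing study medication need to have such assessments done per unplanned assessment eCRF".

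**Leaving the study.** This follows a different route. Under protocol section 6, patients who discontinue the study are scheduled for a visit "at which time all of the assessments listed for the final visit will be performed". If the sponsor ends the study, protocol 5.6.5 says "the patient must be seen as soon as possible and treated as a prematurely withdrawn patient". Both are premature patient discontinuation (PPD), to which footnote A does not apply.

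**Tables.**
- Laboratory, SAP 2.6.2.3.1: "Shift tables based on the standard ranges for each laboratory parameters will be provided by treatment group at each visit".
- ECG, SAP 2.6.2.5: "The number and percentage of patients meeting the following criteria will be summarized by visit and treatment group for the double-blind period". The ECG shift table is also visit-based, and an ECG listing is planned.
- Vital signs, SAP 2.6.2.4: summaries are given "for actual value and change from baseline values for each scheduled assessment visit and treatment group". Notable values are listed.
- Counts not tied to a visit: clinically notable laboratory values (Table 2-4) and liver toxicity criteria (Table 2-7), both worded as post baseline.

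**The concern.** The assessment made when a patient stops drug can be among the more informative safety observations for that patient. The protocol places it outside the planned visit structure, and the SAP builds its ECG outlier and laboratory shift tables on that structure without saying what happens to values recorded elsewhere. Two programmers could follow this SAP and produce different tables.

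The second issue does not depend on unplanned data. For a safety comparison between arms, the natural quantity is the number of patients who ever had the abnormality, for example QTcF above 500 msec. The SAP uses that kind of count for Tables 2-4 and 2-7, but not for ECG criteria or laboratory shifts. With MCP-Mod dropped and efficacy output reduced after early termination (SAP section 4), safety tables carry much of the abbreviated report.

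**Working it through.** The plan gives no figure to reproduce. The check sets the two documents side by side and counts what is covered.

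1. **Who is on the unplanned form.** Patients who stop drug and stay in the study (footnote A). Study withdrawals (section 6) and sponsor-termination stops (5.6.5) are not.

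2. **Is there a rule for their values?** None was found. The available SAP text has no visit window, no rule mapping an unplanned or TD assessment to a visit, and no rule excluding one. It limits the vital sign summaries to scheduled visits but does not use that word for the ECG outlier or laboratory shift tables. Inclusion is therefore undefined. Omission is the likely result, because an unmapped value has no row. The two additional ECGs that protocol 6.5.4 requires when a tracing raises a safety concern are in the same position.

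3. **Would a later visit replace the value?** Not necessarily. After drug stop, protocol 5.6.2 sets a minimum of concomitant treatments and adverse events, by clinic visit or telephone. The TD assessment may be the last laboratory or ECG value the patient has.

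4. **Chemistry coverage.** Table 2-3 lists 24 chemistry parameters, counting direct and total bilirubin separately. Table 2-4 covers 11 of them: ALT, AST, BUN, creatinine, total bilirubin, ALP, sodium, potassium, chloride, calcium and uric acid. So 24 − 11 = 13 have by-visit output only: albumin, bicarbonates, direct bilirubin, cystatin C, eGFR, magnesium, phosphates, total protein, γ-GT, amylase, lipase, serum ketones and beta hydroxybutyrate. Table 2-7 uses ALT, AST, total bilirubin and ALP, all already among the 11, so the 13 remain. The white cell differentials and the urinalysis parameters are also absent from Table 2-4.

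5. **ECG coverage.** SAP 2.6.2.5 lists 13 criteria: five for QTcF, three for PR, three for QRS and two for heart rate. None has an any-time count.

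6. **What by-visit rows can give.** Let r₁, …, r_K be the patients in one arm meeting a criterion at visits 1 to K, and N the number who ever meet it at those visits. A patient abnormal at two visits is in two rows, so the table fixes only max(r_k) ≤ N ≤ Σ r_k. If a further u patients meet the criterion only at an unplanned, unmapped assessment, the true number is N + u, and the table does not show u.

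7. **How many patients.** The documents give no rate of stopping drug while staying in the study. As an assumption only, 5% to 20% of the planned arms would be 0.05 × 124 ≈ 6 to 0.20 × 124 ≈ 25 patients at 50 mg, and 0.05 × 62 ≈ 3 to 0.20 × 62 ≈ 12 at each lower dose. The study ended early and the SAP does not give the number randomized, so actual numbers may be lower.

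8. **What cannot be seen.** The laboratory and ECG rows of Table 6-1 are missing from the available text. Protocol 3.6 says hematology and biochemistry are monitored at each study visit after randomization. Nothing visible shows whether an ECG is scheduled at TD. This is a limit of the text, not an error in the plan.

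**The case against.** **Exclusion is not written anywhere.** This stands. A reader might infer that the values at drug stop fall outside the tables, but protocol 5.6.2 calls the occasion a visit, and the two SAP tables do not say scheduled. The documents show only that inclusion is undefined.

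**The population is narrow.** This stands. A reader might extend the point to everyone who stops drug. Footnote A does not reach study withdrawals or sponsor-termination stops, and this SAP exists because the study ended early.

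**Ketoacidosis has its own handling.** This stands. Protocol 5.6.2 lists it among mandatory reasons to stop drug ("Emergence of the following adverse event: Ketoacidosis, diabetic foot ulcer or lower limb amputation"), so a reader might infer that the ketone and bicarbonate values of these patients are lost. But protocol 7.8.1 requires the relevant test results on the adverse event eCRF. SAP 2.6.2.2 gives adjudicated and site-reported cases by arm, plus a listing. The TD visit follows the stop, so its values need not be those of the acute event.

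**Other by-arm output covers the whole period.** This stands in part. Adverse events, including those leading to discontinuation, and events of special interest are tabulated over the double-blind period. Creatinine and total bilirubin, close relatives of eGFR and direct bilirubin, are in Table 2-4. But these tables do not count ECG criteria or laboratory shifts, and a listing gives no count per arm.

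**A one-line mapping rule would do.** It would settle where unplanned values go. It would not supply the any-time count, because step 6 of the working applies even when every value has a row.

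**Conclusion.** The point holds in two parts. First, for patients who stop drug but stay in the study, the SAP leaves undefined whether unplanned values enter the ECG outlier and laboratory shift tables, and omission is likely. Second, these tables cannot give the number of patients per arm who ever had the abnormality. This affects all 13 ECG criteria and all laboratory shifts. For 13 of 24 chemistry parameters there is no Table 2-4 count to fall back on.

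The number of patients affected is unknown. A reader might infer that the arm comparison is biased towards no difference. That would require both omission of the values and more frequent stopping at higher dose, and the documents establish neither. The ECG part of the drug-stop argument also assumes that ECGs are done at TD, which could not be checked. The missing any-time count does not depend on either assumption. This is a cheap improvement, not a flaw that undermines the safety analysis.

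**What to change.** - **SAP 2.6.2.5:** add, by arm, the number and percentage of patients who ever meet each ECG criterion post baseline.
- **SAP 2.6.2.3.1:** add, by arm, a shift from baseline to the worst post-baseline value, in each relevant direction, for the Table 2-3 parameters, at least those not covered by Table 2-4.
- **Both sections:** state that these tables use all scheduled and unplanned assessments (TD and repeats) in the double-blind period.
- Keep the by-visit tables as they are.

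The cost is a few sentences and a few extra tables from data already planned for collection. No procedure or clinical rule changes. There is one small downside: patients with more unplanned tests have more chances of an extreme value, so a footnote should say that unplanned values are included.
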